### **10.3.2 Analysis of Registry Treatment-Emergent SAEs and AEs of Special Interest**

Registry Treatment-emergent SAEs and AEs of Special Interest will be summarized.

Registry Treatment-emergent AEs includes AEs occurring from the first dose day of the registry to 70 days after the last dose of registry drug excluding AEs occurring during TI period. The SAEs and AEs of Special Interest collected through the HCP process will not be included in this summary.

The number and percentage of patients experiencing registry treatment-emergent SAEs and AEs of Special Interest will be tabulated by body system and MedDRA® preferred

term. In addition, a summary of SAEs and AEs of Special Interest by severity and relationship to registry drug will be presented. Rates (event per 100 patient-years of registry exposure to Humira or MTX) of SAEs and AEs of Special Interest and the 95% confidence interval will be provided.

### **10.3.3 Analysis of All Treatment-Emergent SAEs and AEs of Special Interest**

All Treatment-emergent SAEs and AEs of Special Interest includes events occurring after the first recorded (initial) dose of MTX or Humira (after the first recorded dose of study drug in previous study for subjects who rollover from Study DE038 or Study M10-444 into this registry), up to 70 days after the last dose of registry drug (excluding SAEs and AEs of Special Interest occurring during TI period and AEs which occurred during the double-blind period in Study DE038 if the patient was in the Placebo arm during this period). The SAEs and AEs of Special Interest collected through the HCP process will not be included in this summary.

The number and percentage of patients experiencing treatment-emergent SAEs and AEs of Special Interest will be tabulated by body system and MedDRA® preferred term. In addition, a summary of SAEs and AEs of Special Interest by severity and relationship to registry drug will be presented. Rates (event per 100 patient-years of total exposure to Humira or MTX) of SAEs and AEs of Special Interest and the 95% confidence interval will be provided.

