### 6.1.1 Inclusion Criteria

The decision to prescribe either Humira or MTX must be made prior to the decision to enroll a patient in the registry. A patient will be eligible for participation if he/she meets the following criteria:

1. For a patient enrolling into the Humira arm; a pediatric patient diagnosed at any time with moderately to severely active polyarticular or polyarticular-course JIA (defined as arthritis affecting ≥ 5 joints at the time of diagnosis of polyarticular or polyarticular-course JIA) who has been prescribed Humira therapy according to the locally approved Humira product labeling and meets one of the following criteria:
  - a. Enrolled patients are 4 to 17 years of age as per approved Humira product label with the addition of polyarticular JIA patients 2 to < 4 years of age in countries with available local approval for this group of patients at the time of consent to the registry.
  - b. Newly initiated (within 24 months of registry entry) on Humira therapy and has received continuous (no more than 70 consecutive days off drug) Humira therapy, and the physician can provide available source documentation of SAEs, AEs of Special Interest, and dosing information since initiation of therapy;
  - c. Or is entering after participation (within 24 months of registry entry or, if longer, continuously treated at the same site) in an AbbVie Humira sponsored study, regardless of age or the number of joints with symptoms of polyarticular JIA, and has received continuous (no more than 70 consecutive days off drug) Humira therapy and the physician can provide available source documentation of SAEs, AEs of Special Interest, and dosing information since initiation of therapy.
2. For a patient enrolling into the MTX arm; a pediatric patient diagnosed at any time with moderately to severely active polyarticular or polyarticular-course JIA (defined as arthritis affecting ≥ 5 joints at the time of diagnosis of polyarticular or

polyarticular-course JIA) who is prescribed MTX therapy alone or in combination with other DMARDs according to the local product labeling (initiated treatment within 24 months of registry entry) and has received continuous therapy and the physician can provide available source documentation of SAEs, AEs of Special Interest, and dosing information since initiation of therapy.

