## **6.6 Registry Conduct**

Physicians will be provided with a registry kit that includes a protocol, parental informed consent and patient assent forms, and information material to enable access to electronic Case Report Forms (eCRF), including Serious Adverse Event (SAE) Report Forms, and specially designed eCRFs to collect assessment data and AEs of Special Interest (AESI). When applicable, information about the effectiveness of Humira therapy will be provided by the patients and their physician. Effectiveness of therapy provided by the patient will be collected with paper patient questionnaires and visual analogue scales called patient reported outcomes (PROs) for selfadministered assessments, if part of routine clinical care. Physicians will determine the appropriate therapy for each patient in accordance with the locally approved label. The decision to prescribe Humira (monotherapy or combination therapy with MTX) or MTX (without Humira) to the patients should be made separately from the decision to enroll them into the registry.

The physician will follow the patient during regular office visits at intervals as determined by routine clinical practice or as recommended by national guidelines.

At the enrollment (baseline) visit, the Investigator will complete the Enrollment eCRFs by obtaining and recording all of the available required information. AEs of Special Interest (Section 7.1.3) in addition to hospitalizations and surgeries meeting SAE criteria (Section 7.1.4) that occurred prior to the enrollment (baseline) visit will be collected on a specially designed questionnaire for entry into EDC.

At subsequent visits corresponding to the intervals in the registry activities (Table 1), the Investigator will complete the appropriate eCRF by obtaining and recording all available

[figure not shown]

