**Figure 3. Treatment Period and Treatment Interruption (TI) Period**

## 10.2 Demographics and Registry Enrollment Characteristics

Baseline characteristics: age, sex, race/ethnicity, weight, height, duration of JIA, JIA disease activity and onset type of JIA Disease onset, Rheumatoid factor (RF+, RF-), HLA-B27, body mass index (BMI), prior therapies for JIA, concomitant polyarticular JIA medications, and Humira dosage and exposure duration.

Demographics and baseline characteristics will be summarized for the All Treated Patient Population. Descriptive statistics for demographics, effectiveness, and safety parameters will be presented. Number of patients with non missing values, mean, and standard deviation will be provided for continuous variables. Counts and percentages will be provided for categorical variables. The number and percentage of patients who discontinue from the registry will be summarized, overall and by reason for discontinuation. Duration of observation in the registry, registry exposure duration and total exposure duration will be summarized as follows:

Duration of observation period = the last date of registry participation (inclusive of HCP process) – enrollment date to MTX or Humira in the registry + 1

Registry exposure duration:

(MTX arm) = last MTX dose date in the registry or the first Humira dose date in the registry whichever is earlier – first MTX dose date in the registry + 1 (The first MTX dose in the registry will be on or after the enrollment date).

(Humira arm) = last Humira dose date in the registry – first Humira dose date in the registry + 14 days – total days of any treatment interruptions (The first Humira dose in the registry will be on or after the enrollment date).

Total exposure duration:

(MTX arm) = last MTX dose in the registry or the first Humira dose date in the registry whichever is earlier – first recorded MTX dose (initial dose) + 1.

(Humira arm) = last Humira dose date in the registry – first recorded Humira dose (initial dose) + 14 – total days of any treatment interruptions. For patients who rolled over from Study DE038 and were in the Placebo arm during the double-blind period of this study, the duration of the double-blind period will be subtracted from total exposure.

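### The All Treatment-Emergent rate in Section 10.3.3 is biased low for death and treatment-ending events, because its denominator includes pre-registry time in which those events could not occur

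*Supplement*

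**What the plan says.** The supplement shows the protocol, and the rule is set there. No separate analysis plan is shown.

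- **Numerator.** Section 10.3.3: "All Treatment-emergent SAEs and AEs of Special Interest includes events occurring after the first recorded (initial) dose of MTX or Humira". For patients from Studies DE038 and M10-444 this means the first dose in the earlier study.
- **Denominator.** Section 10.3.3: "Rates (event per 100 patient-years of total exposure to Humira or MTX) of SAEs and AEs of Special Interest". Section 10.2 starts total exposure at the same point: "first recorded Humira dose (initial dose) + 14" in the Humira arm, less interruptions, and "first recorded MTX dose (initial dose) + 1" in the MTX arm.
- **Entry.** Section 6.1.1 admits a Humira patient who is "Newly initiated (within 24 months of registry entry) on Humira therapy and has received continuous (no more than 70 consecutive days off drug) Humira therapy". A patient from an earlier sponsor study may enter "within 24 months of registry entry or, if longer, continuously treated at the same site", and continuous therapy is again required. MTX patients may also have started up to 24 months before entry and need continuous therapy.
- **Population.** Section 10.1 analyses only patients dosed in the registry.
- **Event types.** Death is a serious adverse event (SAE, Section 7.1.4). Any event that ends treatment prematurely is an adverse event of special interest (AESI, Section 7.1.3).

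Section 10.3 lists four safety summaries and ranks none above the others.

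**The concern.** A patient who died before entry, or who stopped the drug for good, never reaches the dataset. Patients who do reach it contribute all their earlier time on drug. For these outcomes that time is immortal: it is in the denominator, but the design excludes the matching events. Nothing in the protocol applies delayed entry to this rate or names the limitation.

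Long-term safety is the primary objective (Section 5.0), and the registry is a post-marketing commitment to two regulators (Section 4.0). Of the two treatment-emergent tables, this one has the larger exposure. A reader could take it as the fullest account of risk on drug, although it is too low for the gravest outcomes.

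**Working it through.** **1. The plan's own figures.** Section 10.6 gives 500 Humira patients, about 68% dropout over five years and about 1,500 PY. With exponential dropout the yearly hazard is −ln(0.32)/5 = 0.228, and 500 × 0.68/0.228 ≈ 1,492 PY, so the 1,500 reproduces. The stated power of about 97% (4.8 against 2.8 events per 100 PY) also reproduces: 42 events expected under the null and 72 under the alternative, rejection at 56 or more, exact Poisson power 97.8%. The present point does not depend on that power.

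**2. Exposure to Year 10.** SAEs, and events related to or ending treatment, are collected to Year 10 (Section 6.0; Table 1, note f), as are dosing data (Section 6.6.11). If the same dropout continued (an assumption), registry exposure would be 500 × (1 − 0.32²)/0.228 ≈ 1,970 PY.

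**3. Dilution.** Let R be registry PY and P pre-registry PY. An event type that blocks enrolment has d events in the registry and none before it. The reported rate is d/(R + P) against d/R, so it is too low by P/(R + P). The mean pre-registry time below is assumed.

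| Mean pre-registry time (years) | P = 500 × mean | Too low, R = 1,500 | Too low, R = 1,970 |
|---|---|---|---|
| 0.25 | 125 | 7.7% | 6.0% |
| 0.5 | 250 | 14.3% | 11.3% |
| 1 | 500 | 25.0% | 20.2% |
| 2 | 1,000 | 40.0% | 33.7% |

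The last row takes the 24-month limit for new patients as the mean and is an extreme. A patient enrolled at the first dose contributes no bias.

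**4. MTX arm.** Section 10.6 gives no MTX person-years. At the same 1,500/500 = 3 PY per patient, 300 patients give 900 PY and the same percentages. For a mean of 1 year: 300/(900 + 300) = 25%.

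**5. Simulation.** Pre-registry time was uniform on 0 to 2 years, registry follow-up at most 3 years, and the terminal hazard 10 per 100 PY throughout. The total-exposure rate was 7.3 per 100 PY; the registry-only rate and the rate in all initiators were both 10.0. With the pre-registry hazard halved or doubled, the total-exposure rate was 0.84 or 0.57 of the all-initiator rate, so it was too low in each case.

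**6. A partial offset.** Events count to 70 days after the last dose, but Humira exposure runs only to 14 days after it. The gap is at most 500 × 56/365.25 ≈ 77 PY, which cancels the dilution only if mean pre-registry time is below 77/500 ≈ 0.15 year. The Registry Treatment-Emergent rate has the same tail, so the offset does not explain a difference between the two tables.

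**7. A boundary case.** An event that began before entry and ended treatment only afterwards can appear in the pre-registry numerator if it is dated by onset. Events that ended treatment before entry cannot.

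**The case against.** The strongest reply is that the plan already reports rates free of this problem. The Observational summary (10.3.1) starts on the first registry day and the Registry Treatment-Emergent summary (10.3.2) at the first registry dose, and both carry 95% confidence intervals. Nothing makes 10.3.3 the lead estimate. Counting from the first dose also has a purpose: it recovers early non-terminal events that an in-registry rate misses in patients enrolled later. All of this stands, and it limits the harm. It does not correct a rate that will be published with its own interval and no caveat.

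Four stronger readings are tempting, and the documents do not support them.

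- **That all serious event rates are too low.** SAEs and AESI that did not stop treatment can be recovered retrospectively. This includes serious infections, on which the sample size rests, where they did not end treatment or prove fatal.
- **That the bias is 40%.** This needs every new patient to enrol at the last permitted moment, or enough long-exposed roll-over patients to lift the mean to two years. The documents give neither the share of such patients nor their exposure.
- **That the Humira–MTX contrast is distorted by a known amount.** Both arms carry pre-registry time. Only the Humira arm takes patients from earlier studies, so a differential is possible, but its size cannot be derived. The protocol sets no between-arm test for these rates.
- **That other pre-registry SAEs go uncounted.** The Section 6.6 questionnaire covers AESI "in addition to hospitalizations and surgeries meeting SAE criteria (Section 7.1.4) that occurred prior to the enrollment (baseline) visit". But Sections 6.6.2 and 9.0 provide for retrospective SAEs generally, and Section 6.1.1 requires that available source records of SAEs can be supplied. This is a mismatch of wording and separate from the bias.

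**Conclusion.** The point holds for one of the four summaries and for two kinds of event: death, and events that permanently end treatment. For these, the Section 10.3.3 rate is biased low in both arms by construction. In the Humira arm the shortfall is about 8% to 25% on 1,500 registry PY, or about 6% to 20% on roughly 1,970 PY, for a mean pre-registry exposure of 0.25 to 1 year. The extreme is 40% (34% on 1,970 PY).

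These figures rest on an assumed mean exposure and, for the longer horizon, on dropout continuing at the same rate. The direction rests only on the entry and exposure rules, apart from the small tail offset when mean pre-registry time is very short. This is a correctable fault in a table that serves the primary objective. It does not invalidate the registry's safety results.

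**What to change.** In Section 10.3.3:

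1. For deaths and events leading to permanent discontinuation, count both events and person-time from registry entry only (delayed entry). State whether an event that began before entry but stopped the drug after it is dated by onset or by the stop date.
2. For all other SAEs and AESI, show events and person-years split at enrolment.
3. State the limitation in the text and as a table footnote.

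The enrolment and dose dates are already needed for the Section 10.2 formulas, so nothing new is collected. For the first group the event count is essentially unchanged, and the rate and both confidence limits rise by the factor (R + P)/R; with a mean of 1 year on 1,500 PY this is 2,000/1,500 = 1.33. The interval is wider in absolute terms by the same factor. The corrected entry will then largely match the one in Section 10.3.2.

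Separately, and as wording only, bring the description of the retrospective questionnaire in Section 6.6 into line with Sections 6.6.2 and 9.0.

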### **10.3.4 Analysis of Patients with Treatment Interruption (TI)**

The following summaries will be performed for patients with a treatment interruption (TI) in Humira injections. The SAEs and AEs of Special Interest collected through the HCP process will not be included in these summaries.

For the first group of safety summaries, all patients will be categorized into 2 groups: patients who have at least one TI and patients who have no TI. Two summaries of SAEs

and Adverse Events of Special Interest will compare descriptively patients who have at least one TI and patients who have no TIs:

Crude incidence: The number and percent of patients experiencing SAEs or Adverse Events of Special Interest will be tabulated for each SOC and PT.

Events per 100 patient years of observation: The number of SAEs and Adverse Events of Special Interest per 100 patient years of observation will be tabulated for each SOC and PT.

For the second group of safety summaries the longest TI will be considered and adverse event rates (SAE and Adverse Events of Special Interest) during the last on-drug period prior to the TI (i.e., the pre-TI period) will be compared to adverse event rates during the first on drug period following the TI (i.e., the post-TI period).

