## **6.2 Patient Follow-up Criteria – HCP Process**

Patients who discontinue full registry participation prior to completing the registry 10 years of follow-up will be offered to participate in the direct to HCP (Health Care Provider) follow-up process, as allowed by applicable local regulations. In order to participate in the direct to HCP follow-up process, the parent or guardian of the patient must sign and date the consent/patient authorization form. Pediatric patients will be included in all discussions as per applicable local regulations in order to obtain verbal or written assent. Patients participating in the HCP follow-up process may not switch registry treatment arms during the HCP follow-up process. To switch to the Humira arm (add on or switch to Humira), an MTX patient following the direct to HCP follow-up process must re-consent at a registry investigative site. The treatment arm at the time of patient authorization will be noted. All data collected post authorization will be included in analysis of the treatment arm indicated at the time of patient authorization, or until the date the patient re-consents in the registry.

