### **10.3.1 Analysis of Observational SAEs and AEs of Special Interest**

The number and percent of patients experiencing SAEs and AEs of Special Interest during the registry, regardless of whether the AEs are reported during or after the Humira or MTX treatment, will be tabulated by body system and Medical Dictionary for Drug Regulatory Activities (MedDRA®) preferred term. Rates (event per 100 patient year of observation) of SAEs and AEs of Special Interest and the 95% confidence interval will be provided. The AEs summaries will also include SAEs and AEs of Special Interest collected through the HCP process. The last contact date is defined as the last date of registry or direct to HCP process participation, whichever occurs later.

The summaries will be provided using data from the first day in registry through the last contact irrespective of drug treatment duration.

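### The treatment-interruption rate in 10.3.4 leaves out HCP-process events but divides by observation time that, as defined in 10.2, includes the HCP process

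*Supplement*

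**What the plan says.** All references are to the protocol; no separate SAP is shown.

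- **Groups (10.3.4).** "all patients will be categorized into 2 groups: patients who have at least one TI and patients who have no TI". The comparison is described as descriptive.
- **Numerator (10.3.4).** "The SAEs and AEs of Special Interest collected through the HCP process will not be included in these summaries".
- **Rate (10.3.4).** "The number of SAEs and Adverse Events of Special Interest per 100 patient years of observation will be tabulated for each SOC and PT". The section gives no definition of observation time and no cut-off at the end of registry participation.
- **Observation time (10.2).** "Duration of observation period = the last date of registry participation (inclusive of HCP process"; the formula then subtracts the enrollment date and adds 1. This is the only definition of an observation period in the document.
- **Who contributes HCP time (6.2).** "Patients who discontinue full registry participation prior to completing the registry 10 years of follow-up will be offered to participate in the direct to HCP". Under 6.0 that follow-up can run through Year 10.

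**The concern.** A rate is interpretable when every unit of person-time in the denominator is time in which an event would have been counted. In the 10.3.4 rate, HCP follow-up adds to the denominator but cannot add to the numerator. Ascertainment for this table falls to zero at HCP entry, and the clock keeps running.

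The effect of treatment interruptions on safety is named in the secondary objective (5.0), and this is the only table that compares interrupters with non-interrupters on a rate. If one group spends a larger share of its follow-up in the HCP process, its rate is diluted more. The table could then show a difference that does not exist, or hide one that does.

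**Working it through.** **Step 1. Compare the safety rates on numerator and denominator.**

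| Section | HCP events counted? | Denominator | Consistent on HCP time? |
|---|---|---|---|
| 10.3.1 observational | Yes: "The AEs summaries will also include SAEs and AEs of Special Interest collected through the HCP process" | Observation, to last contact: "The last contact date is defined as the last date of registry or direct to HCP process participation, whichever occurs later" | Yes |
| 10.3.2 registry treatment-emergent | No | Registry exposure: "Rates (event per 100 patient-years of registry exposure to Humira or MTX) of SAEs and AEs of Special Interest" | Yes |
| 10.3.3 all treatment-emergent | No | Total exposure | Yes |
| 10.3.4 TI versus no TI | No | Observation; by 10.2 this includes HCP time | **No** |

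Section 10.3.4 pairs the exclusion used in 10.3.2 and 10.3.3 with the denominator used in 10.3.1.

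**Step 2. Is there a plan figure to reproduce?** The plan gives no expected rate or ratio for the TI comparison. Its one computed figure, about 97% power in 10.6, does reproduce: 42 versus 72 expected events in 1,500 patient-years gives 97.8% with an exact Poisson test. The present point does not depend on it.

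**Step 3. Size of the dilution.** Let *h* be the share of a group's observation time spent in the HCP process.

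- Reported rate = true registry-phase rate × (1 − *h*)
- Reported ratio = true ratio × (1 − *h*_TI) / (1 − *h*_noTI)

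If *h* = 0 in a group, its rate is unaffected. If *h* is equal in both groups, both rates fall and the ratio is unchanged.

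**Step 4. Illustrations. Every input is an assumption, because the documents give no HCP uptake.** True rates are equal. Stayers have 7 registry years; leavers have 3 registry years and then *k* HCP years. With *f* the fraction who leave for the HCP process, mean registry time is *R* = 3*f* + 7(1 − *f*), and reported/true = *R* / (*R* + *fk*).

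- *k* = 4; *f* = 50% (TI) and 20% (no TI): 5.0/7.0 = 0.714 and 6.2/7.0 = 0.886. Apparent ratio **0.81**.
- *k* = 3; *f* = 30% and 10%: 5.8/6.7 = 0.866 and 6.6/6.9 = 0.957. Apparent ratio **0.905**.
- *k* = 4; *f* = 20% and 50%: 0.886 and 0.714. Apparent ratio **1.24**.

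Wider gaps in *h* do more: 40% against 10% gives 0.60/0.90 = 0.67, and the reverse gives 1.50.

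**Step 5. How large could *h* be overall?** Assume that the 68% dropout allowed for in 10.6 applies, that leavers go at a mean of 2.5 years, and that follow-up runs to Year 10. Mean registry time is 0.32 × 10 + 0.68 × 2.5 = 4.9 years. Mean HCP time is 0.68 × 7.5 × uptake = 5.1 × uptake. With 25%, 50% or 100% uptake, *h* is 1.275/6.175 = 21%, 2.55/7.45 = 34% or 5.1/10 = 51%. A true rate of 2.8 per 100 patient-years (the 10.6 reference rate, used only as an example) would be reported as 2.22, 1.84 or 1.37.

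**The case against.** **The link to 10.2 is inferred.** Section 10.3.4 does not cite 10.2. The 10.2 formula is introduced as a descriptive summary of follow-up, and 10.3.1 states its own end date. A programmer told to leave out HCP events might sensibly stop the clock at registry exit, and an SAP might say so. It is true that the link rests on the shared term. But 10.2 is the only definition available, it expressly includes the HCP process, and nothing in 10.3.4 sets a different end. Silently stopping the clock would depart from the text, so the point is more than a detail left to an SAP.

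**A reader might infer that both rates must be too low and that interrupters will look safer than they are.** The documents do not support that. HCP entry needs separate consent and must be allowed locally (6.2, 6.5). Patients who stop treatment are encouraged to remain in the registry (6.6, 6.8.1). Failure to restart within a year is a listed reason for stopping treatment (6.8.1), but 10.1 also keeps such patients out of the Intermittent Treatment Population. If 10.3.4 follows that population, its TI group consists of restarters, and the larger HCP share could fall in the no-TI group. This objection stands: neither the existence of HCP time in both groups nor the direction of any distortion is known.

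**The table is descriptive and one of several.** This also stands. No test, alpha or decision rule depends on it. Crude incidence has no time denominator, the pre- and post-TI periods have their own windows in Table 2, and the shift table counts patients.

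**Conclusion.** The mismatch holds on the text: the 10.3.4 rate excludes HCP events and, under the only definition given, includes HCP time. Each group's rate is understated by the fraction of its observation time spent in the HCP process, which may be zero. The TI versus no-TI comparison is distorted only if that fraction differs between groups.

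The apparent ratios of 0.81 to 1.24 for a true ratio of 1.00 illustrate the possible scale under assumed uptake; they are not estimates, and they lie on both sides of 1. This should be fixed because the table serves a stated part of the secondary objective. It does not threaten the safety rates in 10.3.1 to 10.3.3, which are consistent on this point.

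**What to change.** In 10.3.4, state that patient-years of observation end at the last date of full registry participation, so that numerator and denominator cover the same time. State also that the HCP-inclusive duration in 10.2 is the rate denominator only for 10.3.1.

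Counting HCP events in 10.3.4 would be an alternative, but a less clean one. HCP collection is narrower than registry collection: AESI, hospitalizations, surgeries and death, with AESI reduced to heart failure and malignancies after Year 5 for most patients (6.0, 6.6.5).

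The cost is one sentence and a derived cut-off date, with no new data collection expected. Section 6.5 has withdrawal and its reason noted on the study completion page but does not mention a date there, so the plan should name the source: registry withdrawal records or the dated HCP authorization (6.2).

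One limit remains. In Years 6 to 10 the registry itself collects only a subset of AESI for patients aged 4 to 17 (6.6.5), and this cut-off does not address that.
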